27.0 STATISTICAL METHODS AND ANALYTICAL PLANS

27.1 Statistical Considerations

Sample size justification

Futility Analysis

Futility analysis is often used for assessing clinical efficacy before the trial reaches target accrual and stops the trial early if the therapy clearly performs worse than control. The primary objective of this one-arm phase II trial is not to evaluate the efficacy of pembrolizumab in this population. Since it is unlikely that the therapy will harm the patients, a futility analysis on the percentage of patients with adequate TIL collection is unnecessary.

Evaluation of Investigational Therapy Safety and Feasibility

Analytic methods

Overview

The primary objective of the single arm phase II trial is to determine whether the surgery feasibility rate of neoadjuvant pembrolizumab is not significantly worse than the historical surgical feasibility rate of neoadjuvant chemotherapy. Surgery feasibility rate of a neoadjuvant therapy is the percent of patients who are able to undertake surgery after the neoadjuvant therapy. A total of 30 evaluable patients will be entered to the single arm trial. Taking 15% rate of cancellation and ineligibility into account, the trial will enroll a total of 35 patients and eligible subjects (not screen failures) will be followed for 2 years for both disease recurrence and death. Following that, patients will be followed every 6 months for up to five years.

Primary Objective Sample Size Justification

According to Pisters et al (JCO 2010), approximately 80% of subjects undergo surgical exploration within 42 days of day 1 of the last cycle of standard neoadjuvant chemotherapy. We would like to test the following hypotheses:

$$H_0: p \geq 0.80 \text{ vs. } H_a: p \leq 0.65$$

where p is the true surgery feasibility rates after combined neoadjuvant chemotherapy and pembrolizumab. With 30 evaluable patients receiving protocol treatment, the study has approximately 84.6% power rejecting $H_0: p \geq 0.80$ when $p = 0.65$ at one-sided significance level of 15%.

Adverse event monitoring: In this trial design it is difficult to accurately attribute adverse events to pembrolizumab, surgery, or other causes. Further, the analysis of treatment toxicities as isolated events will not best represent whether or not the combination of pembrolizumab followed by surgery is safe and feasible. Therefore, this safety and feasibility trial will be evaluated by the following criteria:

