29.2 Appendix B- Correlative Science Measures

Correlative Science Primary Objective

Circulating T Lymphocytes with Specificity Against Tumor Associated Antigens:

Detectable circulating T cells with specificity against TAA will be identified using the following process:

Whenever individual patient tumor tissue is available for analysis, the expression of 10 highly conserved TAA's (see Table I below) will be assessed using standard Real-Time (RT) PCR technology. Peptide pools representing the three most highly expressed TAA's by each tumor will serve as antigen-specific stimulators for PBMC isolated from the same patient at the 4 specified time points. If no tumor tissue is available for TAA expression analysis, peptide pools representing the three most commonly expressed TAA's on NSCLC, namely Survivin, PRAME, and MAGE-A3, will be chosen as antigen-specific stimulators.

The percentage of CD4, CD8, and double positive (DP=CD4+/CD8+) lymphocytes with specificity against the three selected TAA's, will be calculated for each of 4 individual functional markers (IL-2, TNF- α , IFN- γ , and CD107 underlined below). For each peripheral blood collection, the lab will generate a total of 12 lymphocyte values (4 values each for CD4, CD8 and DP) for each of the three TAA's and for CD3/CD28 (used as a positive control), as well as generating 12 background unstimulated negative control values. All values will be expressed as percentages. A patient will be considered to have detectable circulating T cells if ≥ 1 of the 36 percentage values (12 values * 3 TAA's) satisfies the definition of "detectable" as described in section 26.0 (a lymphocyte percentage of $\geq 0.05\%$ at the pre-surgical peripheral blood collection (Collection 3) with each value also being at least twice that of the background unstimulated negative control value).

Table I **TAA Peptide Pools**
(15-mers, overlapping by 11 amino acids)

Survivin (33 peptides)
PRAME/OIP4 (125 peptides)
MAGE-A3 (76 peptides)
Melan A/MART-1 (27 peptides)
Gp100 (163 peptides)
Tyrosinase (117 peptides)
NY-ESO-1 (43 peptides)
MAGE-A1 (75 peptides)
MAGE-A4 (77 peptides)
CEA (173 peptides)

Assessing detectable circulating T cells specific against three TAA's (individually selected from the Table I list of TAA's using the process outlined above) in the following combinations of T cells and functional markers:

- * %**CD4**+/**CD69**+/**IL-2**+
- *%**CD4**+/**CD69**+/**TNF- α** +
- *%**CD4**+/**CD69**+/**IFN- γ** +

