For exploratory outcome 4, changes in all measures of anti-TAA reactivity listed below across time points will be analyzed, as well as how these values relate to pathologic response. In addition, for the phenotypic reactivity measures with background unstimulated negative control values (those from the ICS panel), the percentage of patients with a positive response (a percentage value greater than the background unstimulated negative control value) will be calculated. The distribution of the changes will be estimated with a boxplot and the median (mean) change will be calculated by pathologic response status (yes/no).

%**CD3**+**CD4**+**CD8**- (CD4 T cells)

%**CD3**+**CD4**-**CD8**+ (CD8 T cells)

%**CD3**+**CD4**+**CD8**+ (CD4/CD8 double positive (DP) T cells)

%**CD4**+**CD152**- (CTLA-4 negative CD4 T cells)

%**CD4**+**CD152**+ (CTLA-4+ CD4 T cells)

%**CD4**+/**CD69**+ (Activated CD4 T cells)

%**CD4**+**CD154**+ (Activated CD4 T cells)

%**CD4**+/-**HLA-DR**+ (Activated CD4 cells)

%**CD4**+**CD28**+

%**CD4**+**CD28**-

%**CD4**+/**CD28**+/**CD152**+**CD279**+ (Activated/Exhausted CD4 T cells)

%**CD4**+**CD28**+**CD278**+ (Activated CD4 T cells/Pharmacodynamic Biomarker)

%**CD4**+/**CD25**+**FoxP3**+/**CD152**

%**CD4**+/**CD25**+**FoxP3**+/**CD152**

%**CD4**+/**CD25**+**FoxP3**+/**CD152**

%**CD4**+/**CD25**+**FoxP3**+/**CD152**

%**CD4**+**CD45RA**+**CCR7**+ (Naïve CD4 T cells)

%**CD4**+**CD45RA**-**CCR7**+ (Central memory CD4 T cells)

%**CD4**+**CD45RA**-**CCR7**- (Effector memory CD4 T cells)

%**CD4**+**CD45RA**+**CCR7**- (Effector CD4 T cells)

%**CD8**+**CD152**- (CTLA-4 negative CD8 T cells)

% **CD8**+**CD152**+ (CTLA-4 positive CD8 T cells)

%**CD8**+**CD69**+ (Activated CD8 T cells)

%**CD8**+**CD152**+ (Activated CD8 T cells)

%CD8+/-HLA-DR+ (Activated CD8 T cells)
%CD8+CD28+
%CD8+CD28-
%CD8+/CD28+/CD152+CD279+ (Activated/Exhausted CD8 T cells)

%CD8+CD45RA+CCR7+ (Naïve CD8 T cells)
%CD8+CD45RA-CCR7+Central memory CD8 T cells)
%CD8+CD45RA-CCR7- (Effector memory CD8 T cells)
%CD8+CD45RA+CCR7- (Effector CD8 T cells)

%DP CD69+ (Activated DP T cells)
%DP CD154+ (Activated DP T cells)

%DP CD45RA+CCR7+ (Naïve DP T cells)
%DP CD45RA-CCR7+ (Central memory DP T cells)
%DP CD45RA-CCR7- (Effector memory DP T cells)
%DP CD45RA+CCR7- (Effector DP T cells)

%CD3-SSC^{hi}/HLA-DR^{low}CD14⁺ (Myeloid-derived suppressor cells (MDSC))
FCSxSSC (Monocyte gate)%CD3-CD14- Lin(CD16, CD19, CD20, CD56)- HLA-DR-
CD11b+/CD33+ (MDSC)

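### Appendix B scores any value above the unstimulated control as a positive response, so the percentage of patients positive on an ICS-panel measure largely reflects noise

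*Combined protocol and SAP*

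**What the plan says.** Appendix B (section 29.2) analyses changes over time in a long list of T-cell and MDSC measures for exploratory outcome 4. It then adds a responder summary "for the phenotypic reactivity measures with background unstimulated negative control values (those from the ICS panel"). For these it will calculate "the percentage of patients with a positive response", defined as "a percentage value greater than the background unstimulated negative control value". It does not say which listed markers belong to the ICS panel, or whether positivity is judged for each antigen or across antigens.

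Earlier in the same appendix, a circulating T-cell value counts as detectable only if it is at least 0.05%, "with each value also being at least twice that of the background unstimulated negative control value". That definition applies to "36 percentage values (12 values * 3 TAA's"), with the laboratory "as well as generating 12 background unstimulated negative control values" at each blood collection. The TIL objective in sections 4.2 and 27.1 uses the same two thresholds. Nothing in the documents links the two rules, explains why the looser one is used for outcome 4, or gives the percentage expected without reactivity.

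**The concern.** Without antigen-specific reactivity, the stimulated and unstimulated readings are two noisy measurements of the same quantity. One of them has to be higher unless they tie, and a rule with no margin calls the patient positive whenever that one is the stimulated reading.

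The trial has a single arm, so an absolute percentage positive is likely to be taken at face value. A figure of 40% or 50% would look like substantial reactivity when it is what noise alone produces. True responders would be overstated too. If a fraction r truly respond and all exceed their control, the rule reports about r + (1 − r)/2. With r = 20% that is 0.20 + 0.40 = 60%.

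**Working it through.** The plan gives no expected rate, assay variance or gated-cell count for this rule, so there is no stated figure to reproduce.

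**Inputs from the documents**
- Rule: stimulated percentage greater than unstimulated percentage (Appendix B, outcome 4).
- Control layout: 12 control values against 36 stimulated values per collection (Appendix B, definition of detectable). Since 36/12 = 3, each control serves three antigens.
- Sample: "A total of 30 evaluable patients will be entered to the single arm trial" (section 27.1).

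**Assumption.** With no reactivity, the stimulated value S and the control value B are exchangeable.

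**1. One comparison, continuous readings.** P(S > B) = (1 − P(tie))/2. With no ties this is 0.50, whatever the noise distribution. Simulation with lognormal noise at CVs of 10% to 50% gave 49.9% to 50.0%. In 30 patients this means about 15 positives (95% binomial range 10 to 20). An observed 15/30 has an exact 95% CI of 31% to 69%.

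**2. One comparison, ties allowed.** Background events are assumed Poisson with mean λ. With equal gated-cell counts, ties occur whenever the two counts match. At λ = 1, P(tie) = 0.308, so the rate is (1 − 0.308)/2 = 34.6%. With unequal gated-cell counts, ties are taken to occur only when both counts are zero, and the rate is (1 − e^(−2λ))/2.

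| Expected background events | Equal cell counts | Unequal cell counts |
|---|---|---|
| 0.5 | 26.7% | 31.6% |
| 1 | 34.6% | 43.2% |
| 2 | 39.6% | 49.1% |
| 5 | 43.6% | 50.0% |
| 10 | 45.5% | 50.0% |
| 50 | 48.0% | 50.0% |

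Fifty per cent is therefore the ceiling for one comparison. The rate falls well below it only when background is near zero.

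**3. Any of three antigens against one shared control.** Among four exchangeable values the control is the largest with probability 1/4, so P(at least one antigen exceeds it) = 3/4 = 75%. With ties and equal cell counts it is 61.5% at 1 expected event, 65.7% at 2 and 73.2% at 50. This takes the control layout from the functional-marker values and assumes that it also holds for the outcome 4 measures.

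**4. Effect of a margin.** For the twice-control part alone, with log-scale noise SD σ, P(S ≥ 2B) = 1 − Φ(ln 2/(σ√2)). For assumed σ of 0.2, 0.3 and 0.5 this is 0.7%, 5% and 16%. A simulation of the full rule (at least 0.05% and at least twice control) used Poisson counts and background of 0.01% to 0.5%:

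| Assumed gated cells | Above control | Full rule |
|---|---|---|
| 20,000 to 100,000 | 40% to 49% | 0% to 7.6% |
| 5,000 | 27% to 47% | 1% to 20% |

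The noise SDs, cell counts and backgrounds here are assumptions; none is in the documents.

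**The case against.** The strongest reply is that little depends on this number. It is an addition to an exploratory outcome whose main analysis is change over time and its relation to pathologic response. No test, decision or stopping rule uses it. Sections 4.2 and 27.1 call all secondary objectives exploratory. That stands, and it sets the severity.

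Three stronger readings are tempting, and the documents do not support them.

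- *Half of non-reactive patients will be called positive.* Fifty per cent is a ceiling for one comparison, ties lower it, and pooling three antigens raises it to about 75%. The appendix does not state the counting unit, so no single figure can be given. Later collections may also supply fewer than 30 patients.
- *The result cannot be interpreted, or will contradict the detectable percentages from the same assay.* Blood is drawn at four time points including baseline. If the noise-driven rate is stable, change from baseline still carries information. The measures listed for outcome 4 are phenotypic, and none contains IL-2, TNF-α, IFN-γ or CD107, the markers behind the detectable rule. A shared assay and a conflict between the two percentages are inferences.
- *The detectable rule should simply be copied across.* It does not suit every measure. Where background is already above 0.05%, the floor does nothing. Where background exceeds 50%, twice background would be more than 100% and cannot be reached.

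None of this supplies a reason for having no margin at all.

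**Conclusion.** Wrong as written, of low severity. This is more than missing detail, because following the stated rule exactly produces a misleading percentage. Without reactivity, up to 50% of patients are positive per comparison (about 35% to 48% with ties at 1 to 50 expected background events and equal cell counts, less near zero background). The figure is about 75% if any of three antigens sharing a control suffices.

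The 50% ceiling needs only exchangeability of stimulated and control readings when there is no reactivity. The figures with ties also need the Poisson count model, and the 75% needs the shared-control layout and readings without ties. The fault is confined to the absolute percentage positive. The continuous change analyses, the circulating T-cell and TIL objectives that use the stricter definition, and the surgical feasibility endpoint are not affected.

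**What to change.** In the outcome 4 paragraph of Appendix B:

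1. Name the listed measures that belong to the ICS panel and have an unstimulated control.
2. State the counting unit: each antigen separately, or any of the three.
3. Require a margin. For low-background measures, use at least 0.05% and at least twice the unstimulated control. Take only these thresholds, because the existing definition ties the floor to a value "at the pre-surgical peripheral blood collection (Collection 3"), whereas outcome 4 covers changes across time points.
4. Where background makes the floor or the doubling meaningless or unreachable, prespecify a comparison of stimulated with unstimulated cell counts, with its level.
5. Report the background-subtracted value as the continuous measure, and show the baseline percentage positive beside each later time point.

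The cost is a few sentences and a list of measures from the laboratory, with the same samples and controls. Item 4 also needs gated-cell counts to be kept, since percentages alone will not support it. The downside is that weak true responses below the margin are not counted; the continuous measure still shows them.

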29.3 Appendix C: Performance Status Criteria

ECOG Performance Status Scale		Karnofsky Performance Scale	
Grade	Descriptions	Percent	Description
0	Normal activity. Fully active, able to carry on all pre-disease performance without restriction.	100	Normal, no complaints, no evidence of disease.
		90	Able to carry on normal activity; minor signs or symptoms of disease.
1	Symptoms, but ambulatory. Restricted in physically strenuous activity, but ambulatory and able to carry out work of a light or sedentary nature (e.g., light housework, office work).	80	Normal activity with effort; some signs or symptoms of disease.
		70	Cares for self, unable to carry on normal activity or to do active work.
2	In bed <50% of the time. Ambulatory and capable of all self-care, but unable to carry out any work activities. Up and about more than 50% of waking hours.	60	Requires occasional assistance, but is able to care for most of his/her needs.
		50	Requires considerable assistance and frequent medical care.
3	In bed >50% of the time. Capable of only limited self-care, confined to bed or chair more than 50% of waking hours.	40	Disabled, requires special care and assistance.
		30	Severely disabled, hospitalization indicated. Death not imminent.
4	100% bedridden. Completely disabled. Cannot carry on any self-care. Totally confined to bed or chair.	20	Very sick, hospitalization indicated. Death not imminent.
		10	Moribund, fatal processes progressing rapidly.
5	Dead.	0	Dead.

29.4 Appendix D Standard Cockcroft and Gault Formula for Calculated Creatinine Clearance

Standard Cockcroft and Gault Formula for Calculated Creatinine Clearance

For serum creatinine concentration in mg/dL:

Creatinine clearance (CrCl) will be calculated using the Cockcroft-Gault equation as follows:
$$\text{CrCl (ml/min)} = \frac{(140 - \text{age}) \times (\text{actual weight in kg}) \times 0.85 \text{ for females}}{72 \times \text{serum creatinine (mg/dl)}}$$

[figure not shown]
For serum creatinine concentration in Dmol/L:

$$\text{CrCl} = \frac{[(140 - \text{age}) \times (\text{wt. in kg})]}{[0.81 \times \text{serum creatinine (mol/L)}]}$$
 Females: Multiply the result x 0.85
Units: age in years, weight in kilograms.

Source: Cockcroft DW, Gault MH. 1976. Prediction of creatinine clearance from serum creatinine.

Nephron 16:31-4.

29.5 Appendix E -SITE BIOSPECIMEN PROCESSING FLOW CHART - TOP 1501

29.6 Appendix F-Blood Specimens-Duke

Biomarker Blood Specimens for Correlative Sciences

Duke Processing

Blood will be collected 4 times to assess CD8+ T cells with specificity against tumor antigens. Blood from each of the 4 collections will also be utilized to assess the presence of circulating populations of regulatory T cells, myeloid-derived suppressor cells (MDSC), as well as activated and exhausted T cells.

Blood volumes and collection time points:

At each blood collection, 4 tubes of 8.5-ml each will be collected. The tubes used will be ACD anti-coagulated Vacutainer (yellow tops). The following time points will have blood collections:

Collection 1: Baseline prior to treatment initiation

Collection 2: After dose #2 pembrolizumab prior to surgery

Collection 3: Two to six weeks after surgery prior to initiation of adjuvant therapy

Collection 4: Three to six weeks after the last dose of adjuvant pembrolizumab.

*****If EOS (End of Study) occurs and no adjuvant treatment with Pembrolizumab has occurred, draw Collection #4 at End of Study visit

Once ACD tubes collected, Substrate Services Core lab to be contacted for pick up as PBMC should ideally occur within 4 hours of draw @ [contact]. Tubes are to remain ambient (refrigeration will limit ability to recover PBMC).

DTRI-IM Sample Transport Record form to be completed to accompany tube to the Substrate Services Core lab.

** Note: it is imperative tube is filled to the fill line for proper additive to blood ratio. Specimen is not evaluable if not filled to the fill line. If unable to obtain the 4 required tubes, fill as many tubes as possible to the fill line.

29.7 Appendix G-Blood Specimens-Outside Sites

Biomarker Blood Specimens for Correlative Sciences

Blood samples for biomarker analysis will be collected at four time points and labeled with the Participant Study ID, collection date and time. The blood samples will be collected in four (4) ACD (yellow top) tubes.

Collection 1: Baseline prior to treatment initiation

Collection 2: After dose #2 pembrolizumab prior to surgery

Collection 3: Two to six weeks after surgery prior to initiation of adjuvant therapy

Collection 4: Three-six weeks after last dose adjuvant pembrolizumab

Vacutainer ACD (yellow top) tube: Immediately after drawing the blood, gently invert the tube 5 times. Do not store samples on ice, but hold the tubes at room temperature.

** Note: it is imperative tube is filled to the fill line for proper additive to blood ratio. Specimen is not evaluable if not filled to the fill line. If unable to obtain the 4 required tubes, fill as many tubes as possible to the fill line.

*****If EOS (End of Study) occurs and no adjuvant treatment with Pembrolizumab has occurred, draw Collection #4 at End of Study visit

Sample Storage Prior to Shipment:

The samples should be held at room temperature, and must be shipped the same day the samples are collected.

Sample Shipping:

- It is imperative that samples be shipped according to IATA regulations and in appropriate packaging.
- Samples should be shipped ambient for next morning delivery (priority overnight).
- Samples are to be shipped Monday-Wednesday to be received Tuesday-Thursday (to avoid a late Friday afternoon or weekend delivery). Do not ship samples Thursday through Sunday!
- Email the designated contact prior to shipping to ensure your samples will not be arriving on a university holiday and to confirm that someone will be available to receive the shipment (contact [name]: [contact]).
- Do not ship on a national holiday or a day which is followed by a national holiday.

Shipping address:

Lab Technical Manager

Substrate Services Core Lab

Duke University Medical Center
[name].
[name]
Durham, NC 27710
Phone - [contact]
Fax - [contact]
[contact]

29.8 Appendix H-Tissue Specimens-Duke

Surgical Tissue Specimen for Correlative Sciences Duke Processing

SURGICAL SPECIMEN

Patients will be approached to participate in the “DUHS Biospecimen Repository and Processing core BRPC eIRB 35974” protocol prior to surgery. Tissue will be collected and released as described in this protocol to ensure proper involvement of pathology to minimize the chance that a tissue collection event interferes with appropriate clinical tissue processing and diagnosis.

PRINCIPLE: Lung tissue is harvested in the frozen section or gross dissection area of the surgery pathology suite. The tissue is first examined by a certified anatomic pathologist or surrogate (resident, pathology assistant). Relevant margins are inked, removed and examined by frozen section analysis, if necessary. It is imperative that harvesting tissue for use in research trials does not impeded accurate initial assessment of critical features of the tumor resection, most notable margin status. After the specimen has been processed for margin status, the frozen section assessment of the specimen is complete, a specimen of excess tumor will be released and acquired by the tumor immunology correlative science staff for isolation of tumor infiltrating lymphocytes (TILs) for purposes of this protocol (as much tissue as possible, but a minimum 1 gm).

SPECIMEN: Lung resection specimen

LOCATION: Surgical Pathology Suite

QUALITY CONTROL: Lab guidelines for safe handling of all samples must be followed. All tubes used for specimen processing must be labeled with the unique patient identifier or sample number before transfer of the tissue sample.

29.9 Appendix I-Tissue Specimens-Outside Sites

BACKGROUND:

The ability to obtain high quality Tumor infiltrating lymphocytes (TIL) from fresh tissue is highly dependent on the tissue procurement (requires as much tissue as possible, minimum 1 gm). Delays in tissue processing usually lead to cell death and RNA degradation. Inadequate shipping conditions can also be a major source of pre-analytic variance in downstream applications. The following procedure addresses these issues.

PRINCIPLE:

Tumor tissue is harvested after surgical resection, weighed, kept cold at 4°C in antibiotic-antimycotic containing Holding Medium, and shipped overnight.

EQUIPMENT AND SUPPLIES:

Equipment:

Scale

Supplies:

50 ml sterile conical tube

Parafilm

Recloseable Zip Lock Plastic Bag

IATA Certified Cold Shipper

Reagents:

*Holding Media (50ml): RPMI 1640 plus 10% Human serum, with antibiotic-antimycotic and 2-Mercaptoethanol

RPMI 1640, HEPES	Gibco 22400-089	44.5 ml
Antibiotic-Antimycotic (100X)	Gibco 15240-096	0.5 ml
Human Serum Type AB (Male)	Sigma H4522	5 ml
2-mercaptoethanol	Sigma M6250	0.05 ml

Storage Requirements:

Tissue samples should be kept cold on ice or at 4°C until shipped.

QUALITY CONTROL:

Lab guidelines for safe handling of all samples must be followed. All tubes used for specimen processing must be labeled with the unique patient identifier or sample number before transfer of the tissue sample.

PROCEDURE - STEPWISE:

1. After procurement, weigh the tissue, note the weight on the Sample Processing Request Form, and place it in a sterile 50 ml tube. Fill the tube with Tumor Holding Media and close tightly. Label the tube with the Study Number and Patient ID. Wrap the top with parafilm to prevent spillage.
2. Be sure to fill out the Sample Processing Request Form and include it in the package with the tissue
3. It is imperative that samples be shipped according to IATA regulations and in appropriate packaging that allows shipping with wet ice..
4. Samples are to be shipped Monday-Wednesday to be received Tuesday-Thursday (to avoid a late Friday afternoon or weekend delivery). Do not ship samples Thursday through Sunday! ** Please ship priority overnight.
5. Do not ship on a national holiday or a day which is followed by a national holiday.

Email the designated contact prior to shipping to ensure your samples will not be arriving on a university holiday and to confirm that someone will be available to receive the shipment (contact

